### 8.2.1. Inclusion criteria

To be included in the study population, patients must meet all of the following criteria:

- Aged 40 years or older on the index date  
As 96% of the patients with COPD were aged 40 years or older in the Ministry of Health, Labour and Welfare (MHLW)'s Patient Survey (2017), the target of this study was set at patients aged 40 years or older.
- Patients with records of ICD-10 codes for COPD (J42, J43 or J44), one record at the index date and additional 2 records (outpatient visit or hospital admission) in the 360 days look-back period [index date, index date -360 days]. This criterion is to exclude patients with infrequent visits who may not be COPD patients, and to secure, collection of patient characteristics data in the look-back period.
- At least one record (outpatient visit or hospital admission) with any ICD-10 codes in the 180 days prior to the start date of look-back period [index date – 360 days, index date – 540 days]. This criterion is to secure patient records throughout the look-back period.
- Two study populations will be set up in Trelegy 100 and MITT users, respectively; COPD patients who started Trelegy 100 or MITT between May 22, 2019 and May 5, 2022 (overall users), and subpopulations of the overall users without any triple therapies in the 360-day look-back period (incident users). Pneumonia occurrence in overall users as well as incident users will be calculated to have good generalizability of study results, since incident users will be a part of overall users. The first use of Trelegy 100 or MITT in the identification period will be included as overall cases. The index date for MITT overall users will be the first prescription date after the launch date of Trelegy 100 (May 22, 2019). In the identification of incident users, “any triple therapies in the look-back period” refer to triple therapies with only COPD indication, mixture of COPD and asthma indications, and only asthma indication.

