### 8.3.3. Confounders and effect modifiers

#### 8.3.3.1. Covariates

The following covariates data will be used to calculate the marginal HR for hospitalization due to CAP among incident Trelegy 100 users compared to incident MITT users (primary objective), to characterize target patients (secondary objective-b) and to calculate adjusted HRs for “hospitalization due to CAP” among subgroups within Trelegy 100 or MITT groups (secondary objective-c)).

- **Sex**
- **Age:** Age at index date
- **Calendar year of index date:** Because medical practice changes over time
- **Month of index date (and not the month of hospitalization due to CAP):** Because of seasonal differences in pneumonia occurrence
- **COPD treatments in look-back period**
  - 1) Immediate previous treatment as COPD maintenance therapy (LAMA, LABA, LAMA/LABA, ICS/LABA, ICS/LAMA/LABA or no COPD maintenance therapy): As potential confounding factors
    - Immediate previous therapy will be identified during 180 days before the index date (and not during the entire look-back period).
  - 2) Prescriptions of ICS as treatment of COPD or asthma: As a risk factor for pneumonia occurrence during the look-back period  
Confirm that ICD-10 code for COPD (J42, J43 or J44) or asthma (J45 or J46) is recorded in the receipt of the month which includes prescription of ICS.
  - 3) Prescriptions of oral corticosteroid (OCS) as treatment of COPD or asthma: As a risk factor for pneumonia occurrence during the look-back period  
Confirm that ICD-10 code for COPD (J42, J43 or J44) or asthma (J45 or J46) is recorded in the receipt of the month which includes prescription of OCS.
  - 4) Home oxygen therapy (HOT) for COPD: As an index for COPD severity  
Confirm that ICD-10 code for COPD (J42, J43 or J44) is recorded in the receipt of the month which includes the conduct of HOT.
    - Other therapies (including rescue therapy, xanthine, biologicals) for COPD or asthma will not be included as covariates.

- **History of COPD exacerbation**

In MDV database, hospitalization due to COPD exacerbation (severe COPD exacerbation) will be identified correctly by using DPC data, while it is difficult to identify mild/moderate COPD exacerbation without hospitalization (i.e., without DPC data) because systemic corticosteroids/antibiotics are prescribed for various diseases and prescription data are not linked with disease data one by one.

Hospitalizations due to COPD exacerbation in the look-back period.

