- Definition: Hospitalization due to COPD exacerbation in the look-back period will be identified using DPC data. The following ICD-10 codes, DPC disease classification codes and prescription data will be used.
  - 1) Any of the following ICD-10 codes as DPC disease segment #21 (disease which triggered the hospitalization)
    - Pneumonia-related codes: J10.0, J11.0, J12-J18
    - Acute lower respiratory tract infection-related codes: J20-J22
    - COPD exacerbation-related codes: J44.1
    - Chronic respiratory failure: J96.1
  - 2) Prescription of any systemic corticosteroid combined with any systemic antibiotics at the admission day or the next day. Date of prescription with systemic corticosteroid can be the same as or different from that of antibiotics prescription.

If both of the above 1) and 2) are recorded on the same hospitalization, it is defined as “COPD exacerbation requiring hospitalization”.

Only the presence or absence of the event in the look-back period will be identified.

- **History of pneumonia**

Hospitalization due to CAP in the look-back period

- Definition: Same definition as the outcome measure (see “Sec 8.3.2 Outcome definitions”)
- Only the presence or absence of the event n look-back period will be identified.

■ **Medical history or comorbidities**

The following medical history or comorbidities in the look-back period

- Definition:  $\geq 1$  record (outpatient visit or hospital admission) with relevant ICD-10 codes for each comorbidities in the look-back period [Index date – 360 days]
  - 1) Asthma (ICD-10 codes: J45, J46)
  - 2) Myocardial infarction (ICD-10 codes: I21.x, I22.x, I25.2)
  - 3) Congestive heart failure (ICD-10 codes: I09.9, I11.0, I13.0, I13.2, I25.5, I42.0, I42.5-I42.9, I43.x, I50.x, P29.0)
  - 4) Cerebrovascular disease (ICD-10 codes: G45.x, G46.x, H34.0, I60.x-I69.x)
  - 5) Dementia (ICD-10 codes: F00.x-F03.x, F05.1, G30.x, G31.1)
  - 6) Peptic ulcer (ICD-10 codes: K25.x-K28.x)
  - 7) Peripheral vascular disease (ICD-10 codes: I70.x, I71.x, I73.1, I73.8, I73.9, I77.1, I79.0, I79.2, K55.1, K55.8, K55.9, Z95.8, Z95.9)
  - 8) Connective tissue disease (ICD-10 codes: M05–M08, M30–M36)
  - 9) Diabetes (ICD-10 codes: E10.0-E10.9, E11.0-E11.9, E12.0-E12.9, E13.0-E13.9, E14.0-E14.9)
  - 10) Anxiety (ICD-10 codes: F40-F42)
  - 11) Depression (ICD-10 codes: F32, F33)

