#### 8.7.3.1. Primary endpoints

##### 8.7.3.1.1. HRs for hospitalization due to CAP among incident Trelegy 100 users compared to incident MITT users

To adjust covariates (refer to “8.3.3.1 Covariates”), propensity score which is defined as a probability of Trelegy 100 treatment selection conditional on observed covariates will be estimated for an individual using logistic regression. Multicollinearity will be considered when selecting covariates. By inverse probability of treatment weighted Cox models using the propensity score, the marginal HR along with 95% confidence intervals will be estimated among incident Trelegy 100 users compared to incident MITT users. Variance estimation will be calculated using robust sandwich variance method.

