## 8.9. Limitations of Research Methods

This study uses MDV database which consists of hospital data, and thus only patient data in the hospitals included in MDV database are available. If a patient is treated in hospitals outside of MDV database, treatment records are not available. In MDV database, data can be extracted from health insurance claims and DPCs, but some key data (including smoking history, BMI) are not recorded completely. Based on these characteristics of MDV database, there are some limitations listed below:

- Outcome:
  - It is possible that some pneumonia events requiring hospitalization are recorded outside of DPCs, resulting in underestimation of the outcome measure. If pneumonia requiring hospitalization is treated in hospitals outside of MDV database, such data are not available and outcome measure is underestimated.
  - If data in DPC disease segment #21 (disease which triggered the hospitalization) are incorrect, occurrence of CAP will be overestimated or underestimated.
  - Pneumonia identified by only ICD-10 codes may be overestimated. Addition of prescription of antibiotics and imaging diagnosis to the outcome definition can increase the accuracy, but still there may be some overestimation.
- Risk factors for pneumonia:
  - Old age, lower % predicted forced expiratory volume in 1 second (FEV1), history of COPD exacerbations, worse Medical Research Council (MRC) dyspnea score and lower BMI were treatment-independent risk factors for pneumonia. In MDC database, data of lung function and respiratory symptoms are not available, and BMI data are only partially available.
- Exposure:
  - The reason (e.g., transfer, death) is unknown when Trelegy 100 or MITT prescription records are no longer available after the index date if a patient is treated in hospitals outside of the database. In MDV database, there are no records of the reasons for change in prescription. Dosage information is not available for inhaled drugs, and the estimated daily dose and prescription period could be different from the actual ones.
  - In MDV database, treatment adherence data are not available, and the estimated exposure period could be different from the actual one.
- Study population:

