  - At least one record before the look-back period is required to secure patients records throughout the look-back period, but still there could be some missing data during the look-back period, for example, lack of treatment records in hospitals outside of MDV database.
- Others:
  - Some key data are not available including:
    - Medical history or comorbidities in the look-back period treated at hospitals outside of the

- database
- Pneumonia treatment in the look-back period at hospitals outside of the database.

The results from this study should be carefully interpreted and generalized, however if the above limitations affect both Trelegy 100 and MITT groups to a similar extent, negative impact on the internal validity of the study could be minimum.

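### The primary propensity score has no visit count and no all-cause admission indicator, so any difference between the groups in use of the database hospital, and hence in capture of CAP, is only partly adjusted for.

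*Protocol*

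**What the plan says.** Protocol 8.3.3.1 opens its list with "The following covariates data will be used to calculate the marginal HR for hospitalization due to CAP", and 8.7.3.1.1 builds the propensity score from that list and estimates the HR "By inverse probability of treatment weighted Cox models using the propensity score". The list holds sex, age, index year and month, prior COPD treatment (including ICS, OCS and home oxygen), admission for COPD exacerbation (yes/no), admission for CAP (yes/no), 11 comorbidity flags, BMI, smoking, and whether a lung function test was done. The protocol's stated routes for changing it are multicollinearity (8.7.3.1.1, 8.7.3.4) and more than 10% missing data (8.7.1). Neither adds a variable.

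Each comorbidity needs at least one "record (outpatient visit or hospital admission) with relevant ICD-10 codes for each comorbidities in the look-back period". Entry under 8.2.1 needs "one record at the index date and additional 2 records (outpatient visit or hospital admission) in the 360 days look-back period", plus one record in the preceding 180 days.

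Section 8.9 states of the outcome: "If pneumonia requiring hospitalization is treated in hospitals outside of MDV database, such data are not available and outcome measure is underestimated". It also lists as unavailable "Medical history or comorbidities in the look-back period treated at hospitals outside of the" database. It then argues that "if the above limitations affect both Trelegy 100 and MITT groups to a similar extent, negative impact on the internal validity" could be minimal.

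**The concern.** Two things depend on how much of a patient's care the database hospital provides: whether a CAP admission is seen, and whether a comorbidity is flagged. A patient who attends often is more likely to be admitted there and has more chances to collect a code. The list has no direct measure of attendance, so the weights balance it only through proxies.

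The protocol's defence is a condition, that the limitations act similarly in both groups. None of the three sensitivity analyses in 8.7.3.3 addresses it. The balance table in 8.7.3.2.3 cannot show a difference in visits or all-cause admissions, because neither is among its variables. Section 8.5.1 says that the difference in characteristics between the two groups is not known.

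At stake is the reading of the primary HR against the line of 3. Lower capture in the Trelegy 100 group could hide a signal, and lower capture in the MITT group could create one.

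**Working it through.** **1. Reproduce the protocol's figure.** Inputs from 8.5 and 8.5.1: 3225 Trelegy 100 and 2185 MITT incident users (larger scenario), 10% annual CAP rate, true HR 3.5.

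- Total events D = 0.10 × (3225 + 2185) = 541.
- Trelegy 100 share = 3225 × 3.5 / (3225 × 3.5 + 2185) = 0.838, giving 453.3 and 87.7 events.
- SE(ln HR) = √(1/453.3 + 1/87.7) = 0.1166.
- P(observed HR > 3) = 1 − Φ[(ln 3 − ln 3.5)/0.1166] = 90.7%.

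Table 1 prints 90.7. The same formula matches all 40 cells of Table 1 (those printed as > 99.0 come out at 99.1 to 99.7). The table therefore assumes equal capture.

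**2. Enter unequal capture.** Let c = capture in Trelegy 100 / capture in MITT. With rare events, observed HR ≈ true HR × c, and the Trelegy 100 events in the SE are multiplied by c. The documents give no capture figure, so every c is an assumption.

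To tie c to hospital use, split patients into high and low users. Capture in a group = share high × capture in high + share low × capture in low.

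| Assumed capture, high / low users | Assumed share of high users, Trelegy / MITT | Capture, Trelegy / MITT | c |
|---|---|---|---|
| 90% / 75% | 45% / 55% | 0.8175 / 0.8325 | 0.982 |
| 90% / 60% | 40% / 60% | 0.72 / 0.78 | 0.923 |
| 90% / 60% | 30% / 70% | 0.69 / 0.81 | 0.852 |

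**3. Effect on the decision line** (10% rate; larger scenario, with the smaller 1935/1311 scenario in brackets):

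| c | True HR | Observed HR | P(observed HR > 3) |
|---|---|---|---|
| 1 | 3.5 | 3.50 | 90.7% (84.7%) |
| 0.982 | 3.5 | 3.44 | 87.8% (81.6%) |
| 0.923 | 3.5 | 3.23 | 73.6% (68.8%) |
| 0.852 | 3.5 | 2.98 | 47.9% (48.4%) |
| 1 | 2.5 | 2.50 | 4.1% (8.9%) |
| 1/0.982 = 1.018 | 2.5 | 2.55 | 5.9% (11.2%) |
| 1/0.923 = 1.083 | 2.5 | 2.71 | 16.3% (22.3%) |
| 1/0.852 = 1.174 | 2.5 | 2.93 | 41.6% (43.5%) |

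**4. Break-even.** c = 3/3.5 = 0.857 brings a true HR of 3.5 down to 3. c = 3/4 = 0.75 does so for a true HR of 4. c = 3/2.5 = 1.20 lifts 2.5 to 3. At a true HR of 1, c would have to be 3.

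The shares in step 2 are crude. Whatever part of the imbalance the existing covariates already remove would bring c closer to 1.

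**The case against.** The case against has five parts.

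- **The plan already limits differences in attachment.** Entry needs three COPD records and an earlier record, expressly to drop infrequent attenders. Follow-up stops once the gap between prescription periods exceeds 30 days (8.1, 8.3.1.1), so time at risk accrues only while the hospital keeps supplying triple therapy, plus the grace period. Length of follow-up is tabulated by group (8.3.3.2). This stands in part: it narrows the difference. But the criteria set a floor without balancing use above it, and a patient still prescribed here can be admitted elsewhere.
- **Proxies exist.** Two cause-specific admission flags, home oxygen and the lung function test carry some information on use. BMI and smoking are recorded only after an admission for any reason, so their missingness tracks all-cause admission. This also stands in part. The flags are yes/no disease or severity items, and with more than 10% missing, 8.7.1 allows BMI and smoking to be supplemented or dropped, either of which can lose the hint. A reader might infer that the plan measures no aspect of hospital use; the list does not support that.
- **No difference is shown.** A reader might infer that the primary HR is biased. No part of the protocol shows that use or capture differs between the groups. One could argue that MITT, needing overlapping records of three components, selects patients more tied to the hospital, but that is inference. This stands, and the point is conditional.
- **The threshold of 3 already allows for confounding.** It guards against false signals. It does not guard against a missed one, which lower capture in the Trelegy 100 group makes more likely.
- **The limitation is disclosed.** True, but disclosure neither adjusts for it nor tests the condition in 8.9.

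**Conclusion.** The point holds in a conditional form. The primary propensity score lacks a visit count and an all-cause admission indicator, while the protocol itself says that the outcome and the comorbidity flags are seen only within database hospitals and merely supposes that the groups are alike in this. If baseline use differs between Trelegy 100 and MITT starters after weighting on the current list, the HR is multiplied by the ratio of capture.

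Direction and size are unknown. The range of about 0.85 to 0.98, or its reverse, rests wholly on assumed capture and use shares and on the rare-event approximation. Of the three scenarios, only the most extreme takes a true HR of 3.5 below 3, and only just (0.852 against a break-even of 0.857); the mildest is negligible. The conclusion against the line of 3 is sensitive mainly when the true HR is about 2.5 to 4. The change is worth making because it is cheap and turns a supposition in 8.9 into something partly adjusted for and visible.

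**What to change.** In 8.3.3.1 add two look-back covariates: the number of outpatient visits (in categories or as a spline) and any-cause hospital admission (yes/no). Use both in the propensity score of 8.7.3.1.1 and show both, unweighted and weighted, in the balance table of 8.7.3.2.3. Because the any-cause flag contains the existing exacerbation and CAP admission flags, check their overlap in the multicollinearity review already planned. Leave the rest of the list unchanged.

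The cost is a short addition to the text and two variables derived from the visit and admission records already needed for the 8.2.1 criteria, with slightly more variable weights. The change removes only the part of unequal capture that baseline use predicts, so the limitation in 8.9 should stay, reworded to say what has been adjusted for. If the groups turn out balanced on both variables, that lends some support to the condition on which 8.9 relies.

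### The exacerbation-history code list omits J44.0, and takes J96.1 without J96.0, so look-back admissions triggered by those codes do not count; the effect on the primary HR is probably small

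*Protocol*

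**What the plan says.** Under History of COPD exacerbation, Protocol section 8.3.3.1 sets two conditions that must be met on the same look-back admission.

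- **Trigger code.** The admission must carry "Any of the following ICD-10 codes as DPC disease segment #21 (disease which triggered the hospitalization"). The list has four lines: "Pneumonia-related codes: J10.0, J11.0, J12-J18"; "Acute lower respiratory tract infection-related codes: J20-J22"; "COPD exacerbation-related codes: J44.1"; "Chronic respiratory failure: J96.1".
- **Drugs.** "Prescription of any systemic corticosteroid combined with any systemic antibiotics at the admission day or the next day".

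The result is a yes/no variable over the 360-day look-back. Section 8.3.3.1 names it among the covariates for the primary marginal HR and for the subgroup HRs of secondary objective c). Section 8.7.3.1.1 puts those covariates into the propensity score behind the weighted Cox model.

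Two other statements are relevant. Section 8.3.3.1 says that "hospitalization due to COPD exacerbation (severe COPD exacerbation) will be identified correctly by using DPC data". Entry to the study uses the whole J44 category: "Patients with records of ICD-10 codes for COPD (J42, J43 or J44"). No reason is given for accepting only J44.1 within J44, or only J96.1 within J96.

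**The concern.** The rule plainly means to capture infective exacerbations, because it accepts the stand-alone acute lower respiratory infection codes. The ICD-10 code that combines COPD with such an infection, J44.0, is missing. The same steroid- and antibiotic-treated admission therefore counts if its trigger is recorded as J20 or J44.1, and does not count if it is recorded as J44.0. For respiratory failure, the only code accepted for an acute admission is the one that the protocol itself labels chronic.

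Exacerbation history matters here. Section 8.9 lists it as a treatment-independent risk factor for pneumonia and says that lung function and symptom data are unavailable. A confounder that misses events is only partly adjusted for, even when the misses are equally common in both groups. The closing remark of section 8.9, that limitations affecting both groups alike do little harm to internal validity, therefore does not cover this case. The balance check in section 8.7.3.2.3 cannot reveal the gap either, because it compares the recorded variable. In objective c), missed events sit in the no-exacerbation group and pull its HR towards 1.

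**Working it through.** **Step 1: which trigger codes count** (section 8.3.3.1, with the drug condition met)

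| Segment #21 code | Scored as exacerbation? |
|---|---|
| J10.0, J11.0, J12-J18 | Yes |
| J20-J22 | Yes |
| J44.1 | Yes |
| J96.1 (labelled chronic) | Yes |
| J44.0 | No |
| J96.0 | No |

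The protocol does not print titles for J44.0 and J96.0. Their standard ICD-10 titles are COPD with acute lower respiratory infection, and acute respiratory failure. Because the variable is yes/no, a patient is misclassified only if every exacerbation admission in the look-back falls in the last two rows or under another unlisted code.

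**Step 2: is a correction already planned?** Section 8.7.3.4 foresees updating some codes to the latest ones. That does not extend to adding a code that was never listed.

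**Step 3: illustrative size for the primary HR.** The protocol has no figure to reproduce, and everything here except the group sizes is an assumption.

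- Group sizes: 3225 and 2185 (section 8.5)
- True prevalence of exacerbation history: p_T in the Trelegy 100 group, p_M in the MITT group
- Share of true histories captured: Se, equal in both groups, with no false positives
- CAP hazard ratio for prior exacerbation: 3
- True treatment HR: 1
- No other covariate adjusted for

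Formulas:

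- Share recorded yes, pooled: s = Se × (3225 p_T + 2185 p_M) / 5410
- True history among those recorded no, group g: q_g = p_g(1 − Se) / (1 − p_g Se)
- Standardised relative risk, group g: R_g = 3s + (1 − s)(1 + 2q_g)
- Residual factor on the HR: R_T / R_M

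Worked case, 20% v 10%, Se = 0.7:

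- s = 0.7 × (645 + 218.5) / 5410 = 0.1117
- q_T = 0.06 / 0.86 = 0.0698; q_M = 0.03 / 0.93 = 0.0323
- R_T = 0.3352 + 0.8883 × 1.1395 = 1.347; R_M = 0.3352 + 0.8883 × 1.0645 = 1.281
- Factor = 1.347 / 1.281 = 1.05

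| p_T v p_M | Se 0.9 | Se 0.7 | Se 0.5 | Covariate omitted (Se 0) |
|---|---|---|---|---|
| 20% v 10% | 1.02 | 1.05 | 1.09 | 1.17 |
| 15% v 10% | 1.01 | 1.03 | 1.04 | 1.08 |
| 10% v 15% | 0.99 | 0.97 | 0.96 | 0.92 |

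A deliberately strong case (25% v 10%, hazard ratio 5) gives 1.12 at Se 0.7 and 1.21 at Se 0.5. With full capture the factor is 1.00 in every row.

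**Step 4: comparison with sampling error.** Take equal rates in the two groups and one year of follow-up per patient. The unweighted 95% limits then lie a factor exp(1.96 × √(1/E_T + 1/E_M)) either side of the estimate.

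- 3225/2185 at 14%: E = 451.5 and 305.9, factor 1.16
- 1935/1311 at 8%: E = 154.8 and 104.9, factor 1.28

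**Step 5: illustrative size for objective c).** With prevalence 10% and Se 0.7, the recorded-no group contains a share q = 0.0323 of true histories. A true HR of 3 appears as 3 / (1 + 2 × 0.0323) = 2.8.

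**The case against.** The strongest reply is that the gap is narrow. A reader might infer that severe infective exacerbations in general are scored as no history. The protocol does not support that: those coded as pneumonia, J20-J22 or J44.1 count when the drug condition is met, and one other qualifying admission is enough for a yes. Nothing in the document shows that J44.0 or J96.0 is often recorded as the admission trigger. The capture rates in the working are assumptions about overall sensitivity, not about the share lost to these two codes. All of this stands.

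The residual factors also lean high. The same propensity score holds prior CAP hospitalization, oral and inhaled steroid prescriptions, home oxygen, previous maintenance therapy and asthma, which plausibly recover part of the lost information. Section 8.5.1 sets the HR>3 threshold partly because residual confounding is expected. This stands too, and it limits the point to a minor one.

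Adding J96.0 has a possible cost. Acute respiratory failure is not specific to COPD, so sensitivity may be bought with specificity, and the calculation, which assumes no false positives, cannot test that. J44.0 and J96.0 therefore need different handling.

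Two further readings are tempting and should not be pressed. Whole-category J44 at entry does not contradict a narrower list here, because entry identifies the disease and this covariate identifies an acute admission. The statement that hospitalized exacerbations are correctly identified contrasts them with milder events that leave no DPC record. It is loose wording, not a claim that every event is captured.

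What the reply does not remove is the unexplained asymmetry between J20-J22 and J44.1 on one side and J44.0 on the other.

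**Conclusion.** The point holds in a limited form and is minor. The list as written scores a steroid- and antibiotic-treated admission triggered by J44.0 or J96.0 as no exacerbation, unless another admission qualifies. This leaves some residual confounding in the primary weighted HR and some misclassification in objective c).

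The size cannot be derived from the protocol. With 90% to 50% capture, a CAP hazard ratio of 3 and prevalences of 15% or 20% against 10%, the factor on the HR is 1.01 to 1.09. The direction is unknown: it falls below 1 if exacerbation history is commoner in the MITT group. A factor of this size is below the expected sampling error and unlikely to change the HR>3 reading. The case for J44.0 rests on its standard ICD-10 title, which the protocol does not print. The case for J96.0 is weaker because that code is not COPD-specific.

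**What to change.** - In section 8.3.3.1, add J44.0 to the segment #21 codes for COPD exacerbation, keeping the steroid-plus-antibiotic condition. Check its title against the code list first.
- For respiratory failure, either state why J96.1 is listed without J96.0, or run a sensitivity definition of the covariate that adds J96.0 and note the possible loss of specificity.

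Both changes should be made before the data extraction for the final report. They alter a covariate, not an endpoint, and need no new data. The cost is one added code in the protocol and code list, a re-run of the derivation and, if J96.0 is examined, one extra run of the propensity-score analysis.

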COPD pharmacotherapy is helpful in improving symptoms and QOL, increasing (and maintaining) exercise tolerance and physical activity, and preventing exacerbations. The Global Strategy for the Diagnosis, Management, and Prevention of Chronic Obstructive Pulmonary Disease (2017 Revision), developed by Global Initiative for Chronic Obstructive Lung Disease (GOLD), recommended LAMA+LABA or LAMA+LABA+ICS as a preferred treatment for patients with severe symptoms of COPD and at-risk of exacerbation. The Japanese Respiratory Society (JRS) Guidelines for the Diagnosis and Treatment of COPD, 4th Edition (2013-Amendment) indicated that the mainstay of drug treatment was bronchodilators, and it was recommended that the use of ICS combination drugs be considered when exacerbations of COPD are repeated. Based on these findings, it was considered that ICS plus LAMA+LABA triple therapy should be used in patients with "recurrent exacerbations even with LAMA+LABA " or "patients with severe symptoms even when treated with ICS+LABA." Because the treatment of COPD is long-lasting and many patients get older and take more than one drug for other comorbidities, increasing adherence, such as adherence and treatment continuation rates, is critical for achieving good treatment outcomes. Trelegy 100, a 3-component inhalant, was also developed with the hope of improving patient convenience and contributing to improved adherence. The superiority of Trelegy 100 over UMEC/VI and FF/VI was verified in CTT116855(IMPACT) study, which is a phase 3 joint study, and there were no new safety concerns. Therefore, an application was submitted for marketing approval in Japan for the indication of remission of symptoms of COPD (chronic bronchitis/emphysema) (when concomitant use of ICS, inhaled LAMA, and inhaled LABA is required), and approval was obtained in March 2019.

The JRS Guidelines for the Diagnosis and Treatment of COPD, 5th Edition (2018 Revision) states that ICS-based drugs are used concomitantly with long-acting bronchodilators in asthma-complicated COPD. In general, the risk of developing pneumonia increases with treatments including ICS, so the use of this drug should be carefully determined according to the individual patient's condition.

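### Exacerbation and pneumonia history enter the primary propensity score only as yes/no over 360 days, so recurrence and recency are only partly adjusted, although the same admission records could supply them

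*Protocol*

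**What the plan says.** Section 8.3.3.1 identifies exacerbation history from DPC admissions in the 360-day look-back, using the admission-triggering diagnosis plus a systemic corticosteroid and an antibiotic on the admission day or the next. It then limits the variable: "Only the presence or absence of the event in the look-back period will be identified". The rule for prior hospitalization due to CAP is the same: "Only the presence or absence of the event n look-back period will be identified". No reason is given for dropping number and timing.

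Section 8.7.3.1.1 uses the section 8.3.3.1 covariates in the propensity score for the inverse-probability-weighted Cox model, which gives the primary HR.

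Three other places bear on this:

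- Section 6.1 gives two uses of triple therapy: "recurrent exacerbations even with LAMA+LABA" and "patients with severe symptoms even when treated with ICS+LABA".
- Section 8.9 lists exacerbation history among treatment-independent risk factors for pneumonia, and says that lung function and symptom data are unavailable and BMI only partly available.
- Section 8.2.2 excludes patients with a CAP hospitalization in the 30 days before index. It has no such rule for exacerbation admissions.

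Non-hospitalized exacerbations are left out with a stated reason: "it is difficult to identify mild/moderate COPD exacerbation without hospitalization (i.e., without DPC data"; steroids and antibiotics are used for many diseases and are not tied to a diagnosis.

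**The concern.** With lung function and symptoms missing, exacerbation history is one of the few severity measures left, and the plan coarsens it without need. The protocol itself regards recurrence as a reason for triple therapy, and a yes/no flag cannot show recurrence. Each DPC admission has a date, so count and time since the last event can be derived from records the plan already uses.

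No planned check would reveal a problem. The balance table (section 8.7.3.2.3) covers the listed covariates, and a standardized difference below 10% on a yes/no flag can coexist with an imbalance in number or recency among those flagged yes. None of the three sensitivity analyses in section 8.7.3.3 alters these covariates. What is at stake is avoidable residual confounding in the primary HR and its confidence interval.

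**Working it through.** **1. Which recent admissions escape the 30-day exclusion.** The exacerbation definition accepts pneumonia codes (J10.0, J11.0, J12-J18), J20-J22, J44.1 and J96.1. A pneumonia-coded admission with a J01 antibiotic on day 0 or 1 and imaging also meets CAP Definition 1 (section 8.3.2), so section 8.2.2 removes the patient if it falls within 30 days before index. What remains is mainly admissions coded J20-J22, J44.1 or J96.1. These patients stay in the cohort and are coded like those with remote events.

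**2. Size of the possible bias (assumed inputs).** The documents give no frequency or effect for recurrent or recent events. Assume:

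- a share p of 10%, 20% or 30% of both groups has a hospitalized event, so the flag is perfectly balanced;
- among them, recent or recurrent cases carry HR 3 for CAP and the others HR 1.5, against patients with no event;
- the recent or recurrent share is 40% in Trelegy 100 and 20% in MITT.

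Mean relative hazard among flagged patients:

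- Trelegy 100: 0.4 × 3 + 0.6 × 1.5 = 2.1
- MITT: 0.2 × 3 + 0.8 × 1.5 = 1.8

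Bias factor B = [1 − p + 2.1p] / [1 − p + 1.8p]:

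| p | B | B if the shares are reversed |
|---|---|---|
| 10% | 1.11 / 1.08 = 1.03 | 0.97 |
| 20% | 1.22 / 1.16 = 1.05 | 0.95 |
| 30% | 1.33 / 1.24 = 1.07 | 0.93 |

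With equal shares in both groups, B = 1.

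**3. The plan's own figure first.** Table 1 (section 8.5.1) reproduces with P = 1 − Φ[(ln 3 − ln HR)/SE] and SE² = 1/d_MITT + 1/d_Trelegy, where total events are the rate times all patients, split in the ratio N_MITT : HR × N_Trelegy. For 1935 and 1311 patients at 12%, total events are 0.12 × 3246 = 389.5.

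- True HR 2.5: 83.1 MITT and 306.5 Trelegy events, SE 0.124, P = 7.0% (Table 1: 7.0%).
- True HR 3.5: 63.2 and 326.3 events, SE 0.137, P = 86.9% (Table 1: 86.9%).

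**4. Table 1 with the largest assumed bias.** ln(1.33/1.24) = 0.070.

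| True HR | P(observed HR > 3), no bias | B = 1.07 | B = 0.93 |
|---|---|---|---|
| 1 | 0.0% | 0.0% | 0.0% |
| 2 | 0.0% | 0.2% | 0.0% |
| 2.5 | 7.0% | 18.2% | 2.1% |
| 3.5 | 86.9% | 94.9% | 73.0% |

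**5. Against random error.** SE of ln HR without weighting, from the event counts in Tables 4 and 5:

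- 232 and 157 events (120 per 1000, smaller cohort): √(1/232 + 1/157) = 0.103. The 95% interval is about ×/÷ 1.22, and 0.070 is 0.68 SE.
- 452 and 306 events (140 per 1000, larger cohort): 0.074. The 95% half-width is 0.145, and 0.070 is about half of it.

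**The case against.** **The indication is shared.** A reader might infer that the indication for triple therapy itself goes unadjusted. It does not: both groups are incident triple-therapy users, and recurrent exacerbation is only one of the two uses in section 6.1. That section also cites newer guidance tying ICS to COPD with asthma, and asthma is a covariate. The documents do not show that exacerbation history drives the choice between the two regimens. This stands, and it makes the concern conditional on a difference between the groups.

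**Proxies exist.** The score already includes "Prescriptions of oral corticosteroid (OCS) as treatment of COPD or asthma", ICS use, home oxygen and maintenance therapy in the last 180 days. These carry some information on severity and recent episodes, so the adjustment is partial rather than absent.

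**The outpatient omission is not a contradiction.** Because the OCS rule accepts a prescription when a COPD or asthma code "is recorded in the receipt of the month which includes prescription of OCS", a reader might conclude that the protocol solves the linkage problem in one place and pleads it in another. But that rule labels a treatment and does not establish an acute event. Every patient must also have a COPD record at index and two more in the look-back (section 8.2.1), so a same-month COPD code discriminates little. The omission is a disclosed data limit.

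**The threshold allows for confounding.** Section 8.5.1 treats HR ≤ 3 as no signal partly because key data are missing. That protects the signal call when the true HR is well below 3. It does not correct the reported HR and interval, and it is no reason to discard information already in the records.

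**Conclusion.** The point holds as an inexpensive improvement, not as an error that undermines the study. The coding is fixed in the protocol itself, number and timing are discarded without a reason, and no planned analysis would show whether this matters.

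The factor of 0.93 to 1.07 rests entirely on the assumed prevalence, hazard ratios and twofold difference in shares. Its direction cannot be determined from the documents, and it is 1 if the groups do not differ. It changes the chance of crossing HR 3 materially only for true HRs such as 2.5 or 3.5.

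A much larger bias can be constructed: a residual factor with relative risk 3 and prevalence 40% against 20% in the whole cohort gives 1.8 / 1.4 = 1.29, or 0.78 reversed. Nothing in the documents supports an imbalance of that size, and even that could not carry a true HR of 1 past 3.

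**What to change.** In section 8.3.3.1, replace the presence-or-absence rule for both histories:

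- Number of hospitalized exacerbations in the look-back: 0 / 1 / 2 or more.
- Number of CAP hospitalizations in the look-back: 0 / 1 / 2 or more.
- Time from last exacerbation admission to index: none / within 30 / 31-180 / over 180 days.

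Collapse sparse levels. Include the variables in the propensity score (section 8.7.3.1.1) and the balance table (section 8.7.3.2.3). The none level of the timing variable coincides with a count of zero, so enter timing nested within any event to avoid exact collinearity.

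The cost is a change of protocol wording, which the SAP alone cannot make because the current text is explicit, and which may need PMDA agreement. It adds about four parameters (one per count, two for timing) among 3,246 to 5,410 incident users, with no new data. The exacerbation and CAP variables will overlap, since one pneumonia-coded admission can count in both; the planned multicollinearity check can cover this.

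A monthly outpatient proxy (systemic steroid plus antibiotic with a COPD code) is optional, as a sensitivity analysis only.
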